14.2. COVID-19 Symptom Diary Scoring

| Symptoms | Response Options and Scoring |
|---------------------------------------------------------------------------------------------|-------------------------------------------------------------------------------------------------------------------------------------------|
| What was the severity of your [insert symptoms] at its worst over the past 24 hours? | |
| 1. Stuffy or runny nose | |
| 2. Sore throat | |
| 3. Shortness of breath (difficulty breathing) | |
| 4. Cough | None = 0 |
| 5. Low energy or tiredness | Mild = 1 |
| 6. Muscle or body aches | Moderate = 2 |
| 7. Headache | Severe = 3 |
| 8. Chills or shivering | |
| 9. Feeling hot or feverish | |
| 10. Nausea (feeling like you wanted to throw up) | |
| 11. How many times did you vomit (throw up) in the last 24 hours? | I did not vomit at all = 0/none 1 to 2 times = 1/mild 3 to 4 times = 2/moderate 5 or more times = 3/severe |
| 12. How many times did you have diarrhea (loose or watery stools) in the last 24 hours? | I did not have diarrhea at all = 0/none 1 to 2 times = 1/mild 3 to 4 times = 2/moderate 5 or more times = 3/severe |
| 13. Rate your sense of smell in the last 24 hours | My sense of smell is THE SAME AS usual = 0/none My sense of smell is LESS THAN usual = 1/mild I have NO sense of smell = 2/moderate |
| 14. Rate your sense of taste in the last 24 hours | My sense of taste is THE SAME AS usual = 0/none My sense of taste is LESS THAN usual = 1/mild I have NO sense of taste = 2/moderate |

14.3. Global Impressions Questions

| | |
|------------------------|--------------------------------------------------------------------------------------------------------|
| Return to Usual Health | In the past 24 hours, have you returned to your usual health (before your COVID-19 illness)? Yes or No |
|------------------------|--------------------------------------------------------------------------------------------------------|

| | |
|-----------------------------------------------|------------------------------------------------------------------------------------------------------------------------------------------------------------------------|
| Return to Usual Activities | In the past 24 hours, have you returned to your usual activities (before your COVID-19 illness)? Yes or No |
| Patient Global Impression of Change (PGI-C) | In the past 24 hours, what best describes the overall change in your COVID-19-related symptoms? Much better, A little better, No change, A little worse, Much worse |
| Patient Global Impression of Severity (PGI-S) | In the past 24 hours, what was the severity of your overall COVID-19-related symptoms at their worst? None, Mild, Moderate, or Severe |

14.4. EQ-5D-5L

| | |
|--------------------|----------------------------------------------------------------------------------------------------------------------------------------------------------------------------------------------------------------------------------------------------------------------------------------------------------------------------------------------------------------------------------------------------------------------------------------------------------------|
| Mobility | No problems; Slight problems; Moderate problems; Severe problems; Extreme problems |
| Self-care | No problems; Slight problems; Moderate problems; Severe problems; Extreme problems |
| Usual Activities | No problems; Slight problems; Moderate problems; Severe problems; Extreme problems |
| Pain/Comfort | No problems; Slight problems; Moderate problems; Severe problems; Extreme problems |
| Anxiety/Depression | No problems; Slight problems; Moderate problems; Severe problems; Extreme problems |
| EQ-5D-5L Index | Derived per EQ-5D-5L User Guide [REDACTED] Updated September 2019 Weights used: For US sites: https://euroqol.org/wp-content/uploads/2020/12/US_valueset_SAS.txt For Romania sites: https://euroqol.org/wp-content/uploads/2023/04/Romania_EQ5D5L_valueset_SPSS.txt |
| EQ VAS | Analogue scale: 0 (The worse health you can imagine) to 100 (The best health you can imagine) |

14.5. Imputation Rules

Imputation rules for missing or partial AE start/end dates and times are defined as:

- If Time (start or end) of any AE is missing and corresponding date is also not missing, then impute as 23:59.
- Only Day of AE start date is missing:
 - If the AE start year and month are the same as that for the first dose date, then:
 - If the full (or partial) AE end date is NOT before the first dose date or AE end date is missing, then impute the AE start day as the day of first dose date.
 - Otherwise, impute the AE start day as the first day of the month.
- If Day and Month of AE start date are missing:
 - If AE start year = first dose year, then:
 - If the full (or partial) AE end date is NOT before the first dose date or AE end date is missing, then impute the AE start Month and Day as the Month and Day of first dose date.
 - Otherwise, impute the AE start MONTH as January and the DAY as 1.
- If Year of AE start date is missing:
 - If the year of AE start is missing or AE start date is completely missing, then query site and leave as missing.
- For missing and partial adverse event end dates, imputation will be performed as follows:
 - If only the day of the month is missing, the last day of the month will be used to replace the missing day.
 - If the day and month are missing or a date is completely missing, it will be considered as missing.

Imputation rules for missing or partial medication/therapy start/stop dates are defined below:

- If only Day of start date is missing:
 - If the start year and month are the same as that for the first dose date, then:
 - If the full (or partial) end date is NOT before the first dose date or end date is missing, then impute the start day as the day of first dose date.
 - Otherwise, impute the start day as 1.
- If Day and Month of start date are missing:
 - If start year = first dose year, then:
 - If the full (or partial) end date is NOT before the first dose date or end date is missing, then impute the start Month and Day as the Month and Day of first dose date.
 - Otherwise, impute the start MONTH as January and the DAY as 1.

- If Year of start date is missing:
 - If the year of start is missing or start date is completely missing, then query site and leave as missing.
- For missing and partial end dates, imputation will be performed as follows:
 - If only the day of the month is missing, the last day of the month will be used to replace the missing day.
 - If the day and month are missing or a date is completely missing, it will be considered as missing.

Imputation rules for SARS-CoV-2 viral load and SARS-CoV-2 nucleocapsid antigenemia data:

- SARS-CoV-2 RNA and RNAemia viral load values reported as TND will be imputed with 1 copy/mL (i.e., 0 log₁₀ copies/mL)
- Infectious SARS-CoV-2 viral load values reported as TND will be imputed with 1 TCID₅₀/mL (ie, 0 log₁₀ TCID₅₀/mL).
- SARS-CoV-2 nucleocapsid antigenemia reported as TND will be imputed as 1 fg/mL.
- Numeric values <LLOQ will be set to the LLOQ.
- Numeric values >ULOQ will be set to the ULOQ.
- Values reported as “POS” will be imputed as half of the LLOQ.
- Imputed values will be used in tables and listings will present actual data.

Imputation rules for PK concentrations

- Serum concentrations that are <LLOQ will be treated as zero for PK analyses, except for <LLOQ values observed between 2 quantifiable concentrations and <LLOQ values that occur after the first quantifiable point, which will be set to missing. If consecutive <LLOQ concentrations are followed by quantifiable concentrations in the terminal phase, those concentrations after <LLOQ concentrations will be treated as missing. Missing concentrations will be treated as missing in the PK parameter calculations.

Imputation rules for all other data:

- No other imputations will occur for any data not previously mentioned.

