3.1. Incomplete and Missing Data

Imputation rules for missing dates of prior/concomitant medications, including COVID-19 vaccinations and prohibited medications, and procedures are provided in [Appendix 14.5](#).

Imputation rules for missing AE data are provided in [Appendix 14.5](#).

Data that are continuous in nature but are reported in the form $<x$, $>x$, $\leq x$, or $\geq x$ (where x is considered as the limit of quantitation) will be set to limit of quantitation value with the following exceptions:

- Efficacy endpoint data will be imputed as detailed in [Appendix 14.5](#).
- PK concentrations data will be imputed as detailed in [Appendix 14.5](#).

- Other incomplete/missing data will not be imputed, unless specified otherwise.

All analyses will be conducted using SAS Version 9.4 or higher. Unless otherwise stated, a two-sided test will be used at a significance level (alpha) of 0.05 for all analyses. Two-sided 95% confidence intervals (CI) will be provided when appropriate.

Summary Tables and Figures will be presented by treatment group and will be labelled as follows:

- “EDP 235 [REDACTED]”
- “EDP 235 [REDACTED]”
- “Placebo”

All subject data will be presented in individual subject data listings. Dates will be shown in subject listings as they have been recorded. Unless otherwise stated, unscheduled visit results will be included in date/time chronological order, within subject listings only. All listings will be sorted by subject number, date/time and visit. The treatment group (randomized) as well as subject’s sex and age will be stated on each listing. Unless otherwise stated, data listings will be based on all subjects randomized.

When no data are available for a table or listing, an empty page with the title will be produced with suitable text (e.g., “There are no records for this table/listing.”). For analyses where convergence or the analysis cannot be performed, “NC” (not calculable) will be presented in summary tables.

For the reporting of this study both CDISC SDTM (SDTM Implementation Guide version 3.3 or later) and ADaM (ADaM Implementation Guide version 1.3 or later) standards will be applied.

[REDACTED]

[REDACTED]

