3.4.3. Intent-to-Treat-c (ITT-c)

The Intent-to-Treat (ITT-c) Population includes all subjects in the SAF Population with their SARS-CoV-2 status confirmed by central RT-PCR viral load at baseline \geq lower limit of quantification (LLOQ) and with at least one post-baseline primary efficacy measurement. Subjects will be analyzed as randomized.

The reasons for exclusion from the ITT-c population will be summarized by treatment group using the Safety population.

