5.3. Baseline Disease Characteristics

The following baseline disease characteristics will be presented by treatment group and overall and stratified by age group and duration of baseline COVID-19 symptoms (≤ 3 days or > 3 days and ≤ 5 days) for all subjects in the SAF, ITT-c and PP populations. Additionally, baseline disease characteristics will be listed for all subjects in the SAF population.

- SARS-CoV-2 RNA viral load
- Infectious SARS-CoV-2 viral load
- SARS-CoV-2 RNAemia
- SARS-CoV-2 serostatus
- Respiratory pathogen test
- SARS-CoV-2 variant
- COVID-19 symptom diary total score

- COVID-19 symptom diary severity

SARS-CoV-2 RNA viral load, Infectious SARS-CoV-2 viral load and SARS-CoV-2 RNAemia will also be summarized as positive, negative and missing where either a numeric or “POS” result is considered positive and TND is considered negative.

Baseline SARS-CoV-2 serostatus will be based on Day 1 SARS-CoV-2 anti-nucleocapsid and anti-spike IgG, and IgM antibodies. If at least one qualitative result is positive or IgM > 1.0, the serostatus will be considered positive. In order to be considered negative, all four results must be non-missing, all qualitative results must be negative and IgM equal to “<1.0”.

A description of how symptoms are scored from the COVID-19 Symptom Diary is in [Appendix 14.2](#). The total symptom score and the following severity categories will be presented:

- Only mild symptoms at Day 1
- 1 moderate and no severe symptoms
- 2 or more moderate symptoms and no severe symptoms
- 1 or more severe symptom(s) and no moderate symptoms
- 1 or more severe symptom(s) and 1 or more moderate symptom(s)

6. Treatments and Medications

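### Appendix 14.5 gives numeric results below LLOQ the value LLOQ but POS results half of LLOQ; POS should be defined and one value used within each assay

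*SAP*

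**What the plan says.** Appendix 14.5 has one list of substitution rules for SARS-CoV-2 viral load (RNA, RNAemia and infectious virus) and nucleocapsid antigenemia. Three of its rules bear on low results:

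- Undetected RNA: "RNA and RNAemia viral load values reported as TND will be imputed with 1 copy/mL", that is 0 log10. Infectious virus and antigenemia have matching rules with 1 unit.
- Numeric and below the limit: "Numeric values <LLOQ will be set to the LLOQ".
- Reported as POS: the value "will be imputed as half of the LLOQ".

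The list ends with its scope: "Imputed values will be used in tables and listings will present actual data".

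Three other places matter. Section 5.3, for RNA viral load, infectious viral load and RNAemia, states that "either a numeric or “POS” result is considered positive and TND is considered negative". Section 3.1 sets censored continuous data to the limit of quantitation in general, but makes an exception: "Efficacy endpoint data will be imputed as detailed in" Appendix 14.5. Section 3.4.3 admits to ITT-c subjects "with their SARS-CoV-2 status confirmed by central RT-PCR viral load at baseline" at or above LLOQ.

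**The concern.** Under Section 5.3 a POS result is positive but not numeric. Giving it a value under the limit makes most sense if it means that virus was detected but could not be quantified. A numeric result below LLOQ describes much the same state. Yet one is raised to the limit, above its own reported value, and the other is placed at half the limit. No reason is given.

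This has two consequences wherever an assay yields both formats below LLOQ. Two subjects with equivalent findings get different analysis values. The ordering can also be wrong: a numeric result below LLOQ/2 ends up above every POS result. Within a subject, a numeric sub-LLOQ result followed by POS looks like a fall, and the reverse sequence looks like a rise, without evidence of either.

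The substituted values enter change from baseline (Sections 8.2.7, 8.2.8 and 8.3.6), AUC (8.2.9 and 8.3.4) and the baseline covariate in the ANCOVA and Cox models of Section 8. For RNA viral load in ITT-c the covariate is largely protected, because Section 3.4.3 requires a baseline at or above LLOQ. For RNAemia, infectious virus and antigenemia, baselines below LLOQ can occur within ITT-c.

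**Working it through.** The SAP gives no figure to reproduce here and does not state the LLOQ. The rules of Appendix 14.5 can be applied directly.

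**Gap per sample.** log10(LLOQ) − log10(LLOQ/2) = log10(2) = 0.301. It is the same for any LLOQ; values from 10 to 3,000 copies/mL were tried. With LLOQ = 100 copies/mL (assumed):

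| Reported result | Substituted value | log10 |
|---|---|---|
| Numeric, below 100 | 100 | 2.000 |
| POS | 50 | 1.699 |
| TND | 1 | 0 |

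A numeric result below 50 therefore becomes 100 and ranks above POS at 50.

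**Shift in a visit mean.** Moving numeric sub-LLOQ results from LLOQ to LLOQ/2 lowers an arm's mean by (share of subjects affected) × 0.301. The between-arm difference moves by (difference in shares) × 0.301. The shares are not in the SAP, so these are assumptions:

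| Difference in shares between arms | Shift, log10 |
|---|---|
| 10 points | 0.10 × 0.301 = 0.03 |
| 20 points | 0.20 × 0.301 = 0.06 |
| 30 points | 0.30 × 0.301 = 0.09 |
| 50 points | 0.50 × 0.301 = 0.15 |

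**Shift in one subject's AUC.** Section 8.2.7 gives swab Days 1, 3, 5, 9, 14 and 33, and Section 8.2.9 uses the linear trapezoidal rule. The weight of a visit is half the gap before it plus half the gap after it. Assuming that log10 values enter the AUC, recoding one visit changes the AUC by weight × 0.301:

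| Day | Weight (days) | Change (log10·day) |
|---|---|---|
| 1 | 1.0 | 0.30 |
| 3 | 2.0 | 0.60 |
| 5 | 3.0 | 0.90 |
| 9 | 4.5 | 1.35 |
| 14 | (5 + 19)/2 = 12.0 | 3.61 |
| 33 | 19/2 = 9.5 | 2.86 |

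The late visits, where low results are most likely, carry the most weight.

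**Direction.** If the active arm has more numeric sub-LLOQ results, raising them to LLOQ shrinks the apparent effect. If placebo has more, it enlarges the effect.

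**Endpoints not touched.** Neither substituted value is TND, so the event in time to TND (Section 8.1.1.2) is unchanged.

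**ITT-c.** On reported values, a numeric sub-LLOQ baseline and a POS baseline both fail the criterion. On substituted values, the numeric one equals LLOQ and passes, while POS at LLOQ/2 fails.

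**The case against.** The strongest reply is that POS is undefined, so its equivalence to a numeric sub-LLOQ result is an inference. One list serves four measures, and nothing in the SAP shows a single assay reporting both formats below LLOQ. If each assay used only one, no two subjects on the same endpoint would be treated differently. This stands, and it is why the point is conditional. It does not remove the point: Section 5.3 lists numeric, POS and TND together as result types for the viral load measures, and the rules as written allow the discrepancy.

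It can also be said that setting censored values to the limit is the SAP's general convention and mirrors its rule for values above ULOQ. That is so, but Section 3.1 sends efficacy data to Appendix 14.5, and the convention does not explain why POS is handled differently. Nor do the documents make LLOQ/2 better than LLOQ; consistency needs only one value.

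A reader might infer two stronger claims. One is that the rule biases the trial towards no effect. The SAP does not support this: a working drug also moves subjects on to TND, so at later visits placebo could hold more detected low results. The other is that sub-LLOQ baselines enter ITT-c. That would happen only if population flags were derived after substitution, which the SAP nowhere directs. Section 3.4.3 reads naturally as the laboratory result, and Appendix 14.5 confines substituted values to tables.

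**Conclusion.** The point holds as an unexplained inconsistency in a stated rule, and it is minor. The gap is 0.301 log10 per affected sample for any LLOQ. Its effect on a between-arm mean is about 0.03 to 0.09 log10 under assumed differences in shares of 10 to 30 points, in a direction that cannot be fixed in advance. A single subject's AUC can move by up to 3.61 log10·day if log10 values are used.

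The conclusion assumes that POS means detected but not quantifiable, and that at least one assay reports both formats below LLOQ. The SAP suggests the first without stating it, and leaves the second open. The wording of the ITT-c criterion is an ambiguity worth closing. It is not an error and does not carry the finding.

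**What to change.** In Appendix 14.5, define POS for each assay. Then assign one common value within that assay to every detected result below LLOQ, whether numeric or POS. LLOQ/2 is a convenient choice because the SAP already uses it for POS; another single value would also remove the 0.301 gap. Defining POS should come first, since it may not mean the same for infectivity or antigenemia as for RNA.

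In Section 3.4.3, add as a clarification that the ITT-c criterion is applied to the reported central result before any substitution.

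The cost is about two lines of text, settled before unblinding. If LLOQ/2 is chosen, the downside is a departure, for these data, from the set-to-limit convention of Section 3.1. That section already exempts efficacy data, so it needs no change.
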